Primary and Secondary Endpoint: The primary endpoint we propose for the primary study aim (Aim 1) is the post-treatment pain interference score, operationalized as an average of pain interference ratings made on the twice-daily diaries during the first four days after treatment (i.e., Days 43-46). The endpoint for the secondary study aim (Aim 2) is the post-treatment score at 28 days follow-up, as operationalized as the average of days 67-70 of pain interference ratings on the diaries.

Design and Outcomes

A randomized, 3-group parallel design, 240-subject clinical trial to test the mechanisms of cognitive therapy, mindfulness meditation, and activation skills on individuals with chronic pain who endorse low back pain as a primary or secondary pain problem.

Interventions and Duration

Participants will be randomly assigned to eight (8) telehealth group sessions of (1) cognitive therapy (CT), (2) mindfulness meditation (MM), or (3) activation skills (AS). Treatment groups will meet, on average, twice per week over the Zoom videoconferencing platform. Each session will last for a duration of about 90 minutes. Proposed mechanisms and outcomes will be assessed twice daily during 2-week baseline, 4-week treatment period, and 4-week post-treatment epoch via cue-elicited ecological momentary assessment (EMA); activity level will be monitored during these time epochs via daily monitoring with ActiGraph technology. Macro-level assessments will be conducted at pre- and post-treatment and at 3- and 6-months post-treatment.

The total time involved in the study (excluding between session skills practice) is approximately 35-40 hours over an 8 to 9-month period.

Sample Size and Population

We plan to enroll 300 participants with moderate to severe chronic pain including low back pain as a primary or secondary pain problem to achieve a sample size of 240 completers, with 80 completers in each of the treatment groups.

Enrolled participants who complete the required baseline components (baseline data and demographic questions, pre-treatment extended assessment period, technology training, re-assessment of pain interference for general activities with a score of ≥ 3 for the past 3 months, re-assessment of pain consistency with a response of $\geq 50\%$ of the time in the past 6 months, and a minimum number of EMA surveys during one week of Baseline Monitoring (Days 1-7) will be randomized to one of the three conditions.

A. SPECIFIC AIMS

A1. Problem Statement

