Moderation Hypothesis 1: Baseline levels of catastrophizing will be associated with response to the CT intervention, such that among those participants assigned to the CT intervention, individuals higher in catastrophizing scores at baseline will be more likely to evidence pre- to post-treatment decreases in pain interference than those individuals scoring lower in catastrophizing at baseline. This positive association between baseline catastrophizing and response to CT treatment will be stronger than the association between baseline catastrophizing and response to either the MM or AS treatments (although we would anticipate that all three associations will be positive, because MM and AS treatments are hypothesized to have an indirect effect on catastrophizing, consistent with the Shared Mechanisms Model).

Moderation Hypothesis 2: Baseline activity levels will be negatively associated with response to the AS intervention, such that among those participants assigned to the AS intervention, individuals lower in activity levels will be more likely to evidence pre- to post-treatment decreases in pain interference than those individuals evidencing higher activity levels at baseline. This negative association between baseline activity level and response to AS treatment will be stronger than the association between baseline activity level and response to either CT or MM treatments (although we would anticipate that all three associations will be negative, because CT and MM treatments will have an indirect effect on activity level, consistent with the Shared Mechanisms Model).

Moderation Hypothesis 3: Baseline levels of non-judgment will be associated with response to the MM intervention, such that those participants assigned to the MM intervention who score higher in baseline non-judgmental awareness will be more likely to evidence pre- to post-treatment decreases in pain interference than those individuals evidencing lower levels of non-judgment at baseline. This positive association between the baseline level of non-judgmental awareness and response to MM treatment will be stronger than the association between baseline non-judgmental awareness and response to either AS or CT treatments (although we would anticipate that all three associations will be

positive, because AS and CT treatments will have an indirect effect on non-judgmental awareness, consistent with the Shared Mechanisms Model).

A2d. Additional Exploratory Tests

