In addition to these primary recruitment sources, we will also recruit using social media, online forums, websites, patient advisory networks, and other online mediums that are pertinent to chronic pain. We will also encourage providers, participants, and interested individuals to pass along our study information to others as they see fit.

The recruitment sources described above will provide participants who are representative of the general population with a history of chronic pain and enhance the generalizability of the study results.

D5. Participants

We propose to enroll 300 participants in order to ensure complete data from 240 randomized participants, assuming a very conservative 20% drop-out rate (the dropout rate in our other studies has never reached below 15%). We will monitor the dropout rate on an ongoing basis, and modify the number of participants recruited as needed to ensure a final sample of N = 240 study completers.

Eligibility Criteria

Inclusion Criteria:

- (1) Age \geq 18 years;
- (2) Endorse having low back pain as a primary or secondary pain problem in the past 6 months;
- (3) Meet criteria for having a chronic pain problem (\geq 3 months, with pain experienced on \geq 50% of days in past 6 months);
- (4) Average intensity of chronic pain \geq 3 on a 10-point scale for most days of the previous 3 months;
- (5) Chronic pain interference for general activities \geq 3 on a 10-point scale for the past 3 months;
- (6) Able to read, speak, and understand English;
- (7) If currently taking analgesic or psychotropic medication, medications must have been stabilized for \geq 4 weeks prior to this study; and
- (8) Availability of a telephone, webcam, and microphone through computer or telephone, as well as daily internet access.

Exclusion Criteria:

- (1) Primary pain condition is headache;
- (2) Severe cognitive impairment;
- (3) Current alcohol or substance dependence;
- (4) Active malignancy (e.g., cancer not in remission), terminal illnesses, or serious medical conditions that may interfere with either study participation or with receiving potential treatment benefits (e.g., severe lupus);
- (5) Inability to walk (defined as unable to walk at least 50 yards), which would limit the ability of participants to benefit from the activation skills intervention;
- (6) Significant pain from a recent surgery or injury;
- (7) Pain condition for which surgery has been recommended and is planned;

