Figure 4. SEM model evaluating the "Limit" component of the LAE model

In the model depicted in Figure 4, while significant change in outcome from pre- to post-treatment is expected, it is anticipated that the effect of treatment condition on outcome will be non-significant (i.e., we anticipate that all three treatments will be associated with similar pre- to post-treatment improvements in pain interference, as reflected by non-significant a_1 and a_2 coefficients). However, the LAE model predicts that the post-treatment pain interference score, when controlling for pre-treatment pain interference, will be significantly associated with baseline levels of pain catastrophizing (i.e., path b in the model). We will also test the b coefficient for significance across each of the three moderating variables. The extent to which the effect of the baseline moderator variable predicting outcome varies as a function of treatment will then be evaluated (i.e., the c_1 and c_2 coefficients in Figure 4). These two pathways from condition to path b in the model, when combined and examined as a single parameter, if significant, will indicate the presence of a Treatment \times Moderator interaction. In the event that this interaction effect is identified, post hoc tests will be conducted separately for each treatment condition. Continuing with the example shown in Figure 4, if baseline catastrophizing is found to be negatively associated with subsequent outcome, and this effect is stronger in CT than in MM and AS, then this will be interpreted as lending support for the predictions made with respect to the “Limit” component of the LAE model.

Additional Exploratory Analyses

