With respect to the causal effects of the treatments on the mechanism variables – data are available regarding the effects of treatment on catastrophizing and mindfulness. For example, a paper reporting the results of a study from one of the PIs of the current proposal found a large effect for MM on catastrophizing (pre-treatment mean [SD] = 19.44 [10.81], post-treatment mean [SD] = 10.22 [9.87]; Cohen's d = 0.89)¹¹⁰. Plagge et al.¹⁰⁹ reported large effects for an AS treatment on a measure of catastrophizing (pre-treatment mean [SD] = 32.9 [13.0], post-treatment mean [SD] = 23.9 [10.5]; Cohen's d = 0.76). In a just-completed study, referred to in the previous paragraph, we found large pre- to post-treatment decreases in catastrophizing in participants with chronic pain who received 4 sessions of CT (pre-treatment mean [SD] = 19.38 [10.90], post-treatment mean [SD] = 12.99 [9.76]; Cohen's d = 0.62). In a recently published study by Turner et al.¹¹¹, significant improvement in facets of mindfulness were observed for both a cognitive-behavioral treatment and a mindfulness intervention as compared to the usual care control. Although we were unable to identify any studies that examined the effect sizes associated with any of these treatments on behavioral activity (discovering this will be one of the valuable outcomes of the current proposal), as a group these studies are consistent with our assumptions that MM, AS, and CT treatments have medium to strong effects on key mechanism variables.

With respect to the association between mechanism variables and pain interference, there is a great deal of research reporting strong associations between catastrophizing and pain interference. Consistent with these data, in our recently completed study examining the effects of four psychosocial treatments on pain interference from the same study mentioned previously, the association between pre- to post-treatment change in catastrophizing and change in pain interference was $r = 0.57$ (note: for the r statistic, this represents a large effect). Two published articles present the association between measures of mindfulness and pain interference.^{112,113} These associations ($rs = -0.30$ and -0.35) were both in the medium range. Again, these findings are consistent with our assumptions that mechanism variables can evidence at least medium effects with pain interference.

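### In the LAE moderation analysis path b mixes prognosis with response, so neither it nor its pooled sign should count as evidence; the between-arm slope contrast should

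*Combined protocol and SAP*

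**What the plan says.** Section A2c states Moderation Hypothesis 1 within the CT arm: "individuals higher in catastrophizing scores at baseline will be more likely to evidence pre- to post-treatment decreases in pain interference" than people who score lower. It adds that this association should be stronger in CT than in MM or AS, and that all three arms should show it in the same direction. Hypotheses 2 and 3 do the same for low activity in AS and high non-judgment in MM.

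The Exploratory Moderation Analyses in D6s turn this into a model.

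- The LAE prediction is that "the post-treatment pain interference score, when controlling for pre-treatment pain interference, will be significantly associated with baseline levels of pain catastrophizing", which is path b.
- "We will also test the b coefficient for significance across each of the three moderating variables".
- Variation of that effect by arm (c1 and c2) is then evaluated. If the two are jointly significant, this is read as a Treatment × Moderator interaction and followed by tests within each arm.
- Limit is supported "if baseline catastrophizing is found to be negatively associated with subsequent outcome, and this effect is stronger in CT than in MM and AS".

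The design is "A randomized, 3-group parallel design, 240-subject clinical trial" with no untreated arm. The Précis plans the analysed sample "with 80 completers in each of the treatment groups".

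**The concern.** The hypotheses concern response to treatment. Path b is the association of a baseline variable with later interference, given the pre-treatment score. People who catastrophize more usually have more interference. After adjustment for one imperfectly stable score, they tend to drift back towards that higher level under any treatment. Without an untreated arm, b cannot separate this drift from average response.

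The drift does not treat the three components alike:

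- **Limit:** predicted association with post-treatment interference negative, prognosis positive. They oppose.
- **Activate:** predicted positive, prognosis negative if less active people fare worse (an assumption). They oppose.
- **Enhance:** predicted negative, prognosis negative. They agree.

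A rule that uses b or its sign may therefore favour Enhance and penalize the other two for reasons unrelated to treatment matching. Section I says the moderation findings will feed patient-treatment matching algorithms, and these need differential response.

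**Working it through.** **Plan's own figure.** None is given for the LAE analysis. Table 5 covers the mediation and moderated-mediation tests. Its interaction rows (93, 98, 102) reproduce exactly with f² = 0.15, two tested predictors and power 0.80, but they do not power this analysis.

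**Inputs.** From the plan: 80 completers per arm, N = 240. D6u says of mindfulness: "Two published articles present the association between measures of mindfulness and pain interference", with correlations of −.30 and −.35. For catastrophizing it reports strong associations, but its only figure (r = .57) relates change to change. Assumed: moderator-interference correlation r of .30-.35 or .50 in absolute size; stability s between pre- and post-treatment interference of .6-.9; two-sided alpha .05, unadjusted.

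**Step 1: b with no moderation.** If the moderator is linked to interference only through its stable part, it correlates r with both the pre and the post score, and these correlate s with each other. Then

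partial r = r(1 − s) / √[(1 − r²)(1 − s²)].

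For r = .35, s = .7: .105 / √(.8775 × .51) = .157. Fisher z: .158 × √236 = 2.43, and 2.43 − 1.96 = 0.47, so about 68% of trials reject.

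| s | r = .30 | r = .35 | r = .50 |
|---|---|---|---|
| .6 | 68% | 83% | 99% |
| .7 | 53% | 68% | 97% |
| .8 | 37% | 48% | 85% |
| .9 | 20% | 26% | 53% |

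Simulation (80 per arm) gives 35-83% for r = .30-.35 and 86-99% for r = .50 at s = .6-.8, and 19-52% at s = .9. The CT-versus-others slope contrast is significant in the predicted direction in only 2-4%.

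**Step 2: expected slopes when Limit is true.** Let the CT-only response slope be −.30 SD per SD. Prognosis adds r(1 − s)/(1 − r²) in every arm. The response slope averaged over three arms is −.30/3 = −.10.

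| r, s | Prognosis | Pooled b | CT slope |
|---|---|---|---|
| .35, .7 | +.12 | +.02 | −.18 |
| .35, .8 | +.08 | −.02 | −.22 |
| .50, .7 | +.20 | +.10 | −.10 |
| .50, .6 | +.27 | +.17 | −.03 |

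The pooled slope can be positive although CT works as hypothesised. The CT slope stays negative, but only just in the last row. The difference between arms is −.30 throughout.

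**Step 3: detection under each reading of the sign condition** (simulated, %; runs differ by one or two points).

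| r, s | Contrast alone | and pooled b < 0 | and pooled b significantly < 0 | and CT slope < 0 | and CT slope significantly < 0 |
|---|---|---|---|---|---|
| .35, .7 | 86 | 31 | 1 | 85 | 60 |
| .35, .8 | 95 | 65 | 7 | 95 | 86 |
| .50, .7 | 87 | 3 | 0 | 82 | 23 |

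At r = .50, s = .6 the sign of the CT slope costs about 20 points (79% to 60%). At s = .9 even the pooled sign costs only 2-16 points.

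**Step 4: omnibus or contrast.** At r = .35, s = .7 the planned two-coefficient test with CT lowest detects the effect in about 77%, against 86% for the directional contrast.

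**The case against.** The strongest reply is that b is not the verdict. D6s goes on to c1 and c2 and requires a stronger effect in CT. A reader might infer from Step 1 that the plan will often declare LAE support with no moderation. The documents do not support that: the interaction test keeps its 5% level, and a false Limit verdict occurs in at most about 2% of trials. This part of the reply stands.

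A reader might also infer that the sign condition blocks a true Limit or Activate result. That needs the pooled reading. The sentence follows the within-arm tests, and A2c states the hypothesis within CT, so the CT slope is at least as natural a reading and costs little in most scenarios. But A2c also expects the association in all arms, the preceding text defines b without reference to arm, and Figure 4 is not available to settle it. With dummy coding and the interaction in the model, b could even be the AS slope. The ambiguity remains.

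It is also fair that the sign condition encodes part of Moderation Hypothesis 1. Without it, Limit could be supported when high catastrophizers in CT do worse than low ones, only less so than in the other arms. A contrast with the mean of two arms could also succeed by beating one of them. Both are reasons to report the target-arm slope and the pairwise differences.

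Finally, the stabilities and r = .50 are not in the documents. Baseline diaries run for about two weeks and the primary endpoint averages four days. If such averages are used, stability may exceed .8 and the problem shrinks. D6s also applies Hochberg and Benjamini control, which the calculations omit, and labels these analyses exploratory.

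**Conclusion.** The point holds in limited form. A significant b is listed as an LAE prediction but cannot show response in a trial with three active arms. It mixes prognosis with average response and is often significant with no moderation, at rates that depend on assumed correlations and stability. It does not by itself yield support for a component.

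The harm from the sign condition depends on an unstated choice. It is severe if the condition refers to the pooled slope at stability .6-.8, usually 0-5 points if it refers to the sign of the CT slope, and intermediate to large if the CT slope must be significant. The same asymmetry applies to Activate only if less active people fare worse, for which the plan gives no figure. Because the analysis is exploratory, this is a worthwhile clarification and does not threaten the primary aims.

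**What to change.** In the Exploratory Moderation Analyses of D6s:

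1. Report b as a prognostic association only. Do not use it, or its pooled sign, as evidence for the LAE model.
2. Rest each component on one prespecified slope contrast, target arm against the mean of the other two, in the predicted direction and with its confidence interval. If AS is the reference arm and b its slope, the contrasts are c1 − c2/2 for CT (catastrophizing, predicted negative), c2 − c1/2 for MM (non-judgment, predicted negative) and −(c1 + c2)/2 for AS (activity, predicted positive).
3. Report the target-arm slope and each pairwise slope difference alongside, and state that the target-arm slope includes prognosis.

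The cost is wording: the model and data stay the same. The downside is that the plan can no longer claim overall moderation from b, a claim it cannot support without an untreated arm.

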As indicated, up to three SEMs (one for each mechanism) will evaluate and test for significance of the *a* and *b* coefficients for each mechanism variable that met the Step 1 assumptions described above (i.e., that evidenced at least a small early slope or larger, for at least one of the treatments). The combination of a treatment effect on the mechanism variable (coefficient *a*) and a significant *b* coefficient for a particular mechanism variable (indicating that early change in the mechanism variable predicts a late change in outcome), with *post hoc* tests linking each treatment to its targeted mechanism variable (i.e., CT, MM, and AS having the largest effects on cognitive content, cognitive process, and activity level, respectively) would support the Specific Mechanisms Model. A significant *b* coefficient in light of non-significant *a* coefficients (i.e., the mechanism plays a role in outcome, but all three treatments have a similar impact on the mechanism variable) would support a Shared Mechanisms Model. Thus, together, the significance levels of the *a* and *b* coefficients will address the study aims. In short, the results of the (maximum) six planned statistical tests (i.e., whether or not there are between-group differences in the three early mechanism slopes, and the significance level of the three *b* coefficients) will allow us to evaluate if the three mechanism variables play a role in treatment outcome, and whether this role is shared between the treatments or unique to a subset of them.

Exploratory Moderation Analyses

We also plan to conduct a preliminary test of the LAE model. Specifically, SEM will be used to evaluate the extent to which baseline catastrophizing, activity levels, and non-judgment are respectively associated with response to CT, AS, and MM. Figure 4 below illustrates the statistical approach that we propose to use to evaluate the LAE model. For illustrative purposes, only the role of baseline catastrophizing moderating response to treatment is depicted. As per the above models, the treatment condition variable is represented by two variables: "CTvsOther" (coded as "1" if the participant is assigned to the CT condition, "0" if not) and "MMvsOther" (coded as "1" if the participant is assigned to the MM condition, "0" if not). When considered in the same model (i.e., when controlling for the other), the two variables contain information about all three treatment conditions.

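### The LAE moderation analysis tests a three-arm interaction through one undefined combined parameter; any single-parameter reading serves at least one of the three moderation hypotheses badly, so a 2-df test is needed

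*Combined protocol and SAP*

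**What the plan says.** Section D6s, Exploratory Moderation Analyses, describes the model behind Figure 4. There "the treatment condition variable is represented by two variables": a CT indicator and an MM indicator, each coded 1 for the named arm and 0 otherwise. Both enter together: "When considered in the same model (i.e., when controlling for the other), the two variables contain information about all three treatment conditions".

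Path b carries the baseline moderator to post-treatment pain interference. After b is tested, "The extent to which the effect of the baseline moderator variable predicting outcome varies as a function of treatment will then be evaluated", through c1 and c2. These two paths, "when combined and examined as a single parameter, if significant, will indicate the presence of a Treatment" × Moderator interaction. The section gives no rule for combining them and names no joint test. Follow-up is conditional: "In the event that this interaction effect is identified, post hoc tests will be conducted separately for each treatment condition".

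The hypotheses in section A2c are specific to an arm. For Moderation Hypothesis 1, the association in CT "will be stronger than the association between baseline catastrophizing and response to either the MM or AS treatments". Hypothesis 2 makes the parallel claim for activity level and AS, and Hypothesis 3 for non-judgment and MM. In each case all three arms are expected to show associations of the same sign, with the target arm strongest.

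**The concern.** Three arms have three moderator slopes, and the differences among them take two parameters to describe. A test of one parameter can look in only one direction. Which direction depends on the combining rule, which the plan leaves open, and on the dummy coding, which makes AS the reference arm.

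The choice matters because this test is a gate: if it is not significant, the plan runs no arm-specific tests. A CT-specific or MM-specific moderation effect could therefore go unexamined because the gate was facing another way. Section I expects the moderation findings to feed into later work on matching patients to treatments, so an avoidable false negative has a cost even in an exploratory analysis.

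**Working it through.** **The plan's nearest figure.** No sample size or power is stated for the LAE test. The closest figures are the three interaction rows of Table 5 (section D6u), which concern the primary tests: f² = 0.15, power 0.80, alpha 0.013, 0.010 and 0.008, n = 93, 98 and 102. I used the noncentral F test for an R² increase, with noncentrality f² × N:

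| Numerator df | n at 0.013 | n at 0.010 | n at 0.008 |
|---|---|---|---|
| 1 | 77–78 | 82 | 85–86 |
| 2 | 93 | 98 | 102 |
| 3 | 104–105 | 109–110 | 113–114 |

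(Ranges cover different total numbers of predictors.) Only 2 df reproduces the plan's figures.

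**What c1 and c2 estimate.** Write b_CT, b_MM and b_AS for the arm-specific moderator slopes. AS scores 0 on both dummies, so c1 = b_CT − b_AS and c2 = b_MM − b_AS.

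- Sum: c1 + c2 = b_CT + b_MM − 2·b_AS. This is AS against the average of CT and MM. The mean gives the same test.
- Difference: c1 − c2 = b_CT − b_MM. AS drops out.
- Needed for catastrophizing/CT: c1 − c2/2 = b_CT − (b_MM + b_AS)/2.
- Needed for non-judgment/MM: c2 − c1/2 = b_MM − (b_CT + b_AS)/2.
- Needed for activity/AS: (c1 + c2)/2 = (b_CT + b_MM)/2 − b_AS.

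**Variances.** Let each arm's slope have variance v. Then Var(c1) = Var(c2) = 2v and Cov(c1, c2) = v, so:

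- Var(c1 + c2) = 2v + 2v + 2v = 6v
- Var(c1 − c2/2) = 2v + 0.5v − v = 1.5v

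If only CT departs, by δ, both quantities have expectation δ. The noncentralities are δ²/6v and δ²/1.5v, so the sum keeps one quarter of the available information. The same holds for an MM-only departure.

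**Power.** From the plan: 80 per arm, 240 in all. Assumed: two-sided alpha 0.05, equal moderator variance in each arm, slopes in residual SD per moderator SD (so v = 1/80), and error df 233. At δ = 0.4:

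- Sum: 0.16/(6/80) = 2.13
- CT contrast: 0.16/(1.5/80) = 8.53
- 2-df test: 80 × (2/3) × 0.16 = 8.53

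| Assumed CT-only difference | Sum | 2-df test | CT contrast |
|---|---|---|---|
| 0.2 | 11% | 24% | 31% |
| 0.3 | 19% | 48% | 59% |
| 0.4 | 31% | 74% | 83% |
| 0.5 | 44% | 91% | 95% |

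At a difference of 0.428, chosen to give the 2-df test 80% power, the sum has 34%. A 2,000-run simulation gave 78% and 34%.

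**Other patterns.**

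- AS-only departure of 0.4: the sum has 83%, the 2-df test 74%, and the difference c1 − c2 has 5%, which is alpha.
- All slopes of one sign with CT strongest, as section A2c expects, for example CT −0.5, MM −0.1, AS −0.3: c1 = −0.2 and c2 = +0.2, so the sum is zero. Its power is 5%, against 61% for the 2-df test and 59% for the CT contrast.
- Moving AS to −0.2 in that example gives 11%, 65% and 72%.

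**The case against.** The strongest reply is that a joint test was meant. The stated purpose is to show whether an interaction is present at all, the two dummies are said to carry the information on all three arms together, and Table 5 reproduces only with 2 df. That is a fair reading of the intent. But Table 5 covers the primary tests, and taken literally a single parameter has 1 df. If a joint test was meant, the text misdescribes it and still needs correcting.

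Three stronger readings are tempting, and the documents do not support them.

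- *A reader might infer that the plan sums c1 and c2 and so tests AS against the other arms.* It never says sum. That contrast follows only if the combination is a sum or a mean.
- *A reader might infer that CT-specific or MM-specific effects will usually be missed.* That depends on their size, which the plan does not give for LAE. At f² = 0.15, the one interaction effect size in section D6u, the noncentrality available is 0.15 × 240 = 36. A quarter of that is 9, and the sum would have about 85% power for a CT-only effect. Complete cancellation needs AS exactly midway between CT and MM.
- *A reader might infer that path b is the AS-arm slope presented as an overall association.* That holds only if b is estimated alongside c1 and c2. The text evaluates variation by treatment after b, so b may be fitted first as a pooled association, and Figure 4 was not visible in the text reviewed. Nor does the plan rest its conclusion on b alone: support also requires a stronger effect in CT than in MM and AS.

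It is also true that the analysis is labelled preliminary and will be reported as exploratory. That limits the stakes but does not settle which test should be run.

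**Conclusion.** The point holds in this form: the rule for combining c1 and c2 is undefined, and no 1-df version can represent a three-arm interaction. A sum or mean suits only the activity/AS hypothesis. For an effect confined to CT or MM it keeps a quarter of the noncentrality: at assumed slope differences of 0.3 to 0.5, power is about 19–44%, against 48–91% for a 2-df test and 59–95% for the matching contrast. A difference is blind to an AS-only effect.

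The algebra rests on the stated coding. The quarter share assumes equal slope variance across arms. The power figures also rest on assumed slopes, because the plan gives none for LAE. Since the test gates the arm-specific analyses, the wording should be changed. The consequences stay within an exploratory objective, and no primary or secondary conclusion depends on it.

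**What to change.** In section D6s, Exploratory Moderation Analyses:

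1. Replace the single-parameter test with a 2-df joint Wald or likelihood-ratio test of c1 = c2 = 0. This agrees with the 2 df that reproduce the interaction rows of Table 5.
2. Prespecify one contrast per hypothesis: c1 − c2/2 for catastrophizing and CT, c2 − c1/2 for non-judgment and MM, and (c1 + c2)/2 for activity level and AS.
3. Report the moderator slope in each arm with a confidence interval.
4. State whether b is estimated in the same model as c1 and c2. If it is, say that b is the AS-arm slope.

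The cost is a wording change to the analysis plan. No added data or participants are needed.
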